7.2.1 Electronic Diary

Patients will be issued an eDiary to record all bleeding events and all doses of ~~factors or~~ BPAs administered during the conduct of the study. Entries are to be made in a timely manner, and it is preferred that doses are entered immediately upon administration or within 24 hours. Patients will be prompted to enter bleeding location, severity, causality (spontaneous or traumatic), doses of ~~factors or~~ BPAs, and reasons for dosing (prophylaxis, treatment of a bleeding episode, and preventive dose for anticipated activity). Training of patients should be documented in the appropriate source record.

The Sponsor will review diary entries for data quality to identify issues such as patients who may need retraining on eDiary use and timely entry of bleeding episode information.

Bleeding episodes will be recorded by the patient in the eDiary and reviewed by the Investigator (and Sponsor) continuously for the study duration. The site will contact the patient at a minimum interval of every 2 weeks (± 4 days) per schedule of assessments to review eDiary records and ensure that the patient is utilizing the device appropriately.

Sites will be notified when patients enter initial treatments for bleeding events into their eDiaries. If the dose amount exceeds the recommended dose according to the bleeding episode

management plan, the patient must be contacted as soon as possible, preferably within 24-48 hours of receiving the alert. At the time of contact the patient's clinical condition will be reviewed along with the dose and efficacy of the treatment given, and the Investigator will provide appropriate guidance regarding further management of the bleed. The site will also receive an alert, and must make contact with the patient as soon as possible if a third dose of product is administered for a single bleed, to review clinical condition, the need for further therapy, and appropriate ongoing management of the bleeding episode required to achieve hemostasis.

In addition, patients will be instructed to contact the site if they feel they need to administer ~~factor or~~ BPA at a higher dose level or higher frequency than their bleeding episode management plan recommends, or if more than two doses are required to achieve hemostasis.

Section 7.3.3 Coagulation/Thrombin generation response assessment in ~~factor or~~ bypassing agent prophylaxis period

During the ~~factor or~~ BPA prophylaxis period (before fitusiran treatment), patients will undergo a coagulation and peak thrombin/thrombin generation response assessment with timed blood collections both before and following a dose of their routine ~~factor or~~ BPA prophylaxis doses. The subgroup of Cohort A patients who are not responding adequately to BPA prophylaxis treatment will not participate in this BPA prophylaxis period and will directly start the fitusiran treatment period after the screening period. For these patients, the coagulation and peak thrombin/thrombin generation response assessment are not applicable.

These laboratory assessments are collected for research purposes, will be run centrally, and will not be released to sites or used to guide study conduct or clinical management.

Section 7.5.5.1 Additional laboratory assessments

Additional laboratory assessments will be performed in patients who experience any LFT abnormalities during either the ~~factor or~~ BPA prophylaxis period (BPA prophylaxis period is not applicable for the subgroup of Cohort A patients who are not responding adequately to BPA prophylaxis treatment) or the fitusiran treatment period. Following the occurrence of elevated liver transaminases or other LFT abnormalities per the central laboratory, all assessments in Table 7 will be performed one time, as well as hematology, serum chemistry, LFT, and coagulation assessments from Table 6, AT levels, and other assessments or evaluations per Investigator discretion, as appropriate.

Section 8.1 Determination of Sample Size

Sample size is based on clinical considerations. The overall sample size of 80 patients including approximately 30 patients with inhibitor (Cohort A) and approximately 50 patients without inhibitor (Cohort B) was selected recognizing the limited number of patients with hemophilia, and to yield a reasonably robust estimate of the fitusiran bleeding episode rate and address the secondary objectives, including characterization of safety and tolerability. The proposed sample size is also expected to provide reasonable precision around the ratio of bleeding rate in the

fitusiran efficacy **treatment** period to bleeding rate in the factor or BPA prophylaxis period for both Cohort A and Cohort B. **In the US, only patients from Cohort A will be included.**

Section 8.2.5.1 Primary endpoint

The primary analysis will be performed on the EAS and will include all bleeding episodes occurring in the factor or BPA prophylaxis period (Day -162 to Day -1) and the fitusiran **treatment** period (Day 1 to Day 190). ~~If a patient does not have bleeding episode data collected after Day 28 (eg due to early study discontinuation), the available bleeding episode data starting from Day 1 will be used in the primary analysis.~~ To avoid confounding the treatment effect, bleeding episode data during and after major surgery, antithrombin administration, major trauma, or initiation of prophylaxis treatment with factors or BPAs during the fitusiran treatment period will be excluded from the primary analysis.

The number of bleeding episodes will be analyzed using a repeated measures negative binomial model with fixed effect of treatment period. The logarithm number of days that each patient spends in the treatment period matching the bleeding episode data being analyzed will be included as an offset variable to account for unequal follow-up time due to early withdrawal or surgery. The ratio of bleeding rates in the fitusiran **treatment** period to the factor or BPA prophylaxis period and its 95% CI and p-value will be presented. The p-value should be interpreted with caution. In addition, as a contrast Bayesian analyses will be performed to summarize the point estimates of the posterior probability of a clinically significant treatment effect, along with associated measures of uncertainty. The estimated mean ABRs in these 2 periods along with their 95% CIs will be presented from this model. In addition estimated mean ABR and its 95% CI during the fitusiran onset period and efficacy period (key secondary endpoint) will be presented.

Section 8.2.5.2 Secondary endpoint

Spontaneous bleeding episodes and joint bleeding episodes will be analyzed using the same method as primary analysis of ABR. Summary statistics, including the median and interquartile range, for annualized spontaneous bleeding rate and annualized joint bleeding rate will be reported.

Change in Haem-A-QOL physical health score and total score (in patients ≥ 17 years of age) in the ~~factor or~~ BPA prophylaxis period and fitusiran treatment period will be summarized descriptively. A mixed model for repeated measures analysis may be performed as deemed appropriate.

The bleeding episodes in the fitusiran onset period and in the fitusiran treatment period will be analyzed using a negative binomial model with logarithm of follow-up time in the period as an offset parameter. Summary statistics, including the median and interquartile range, for the ABR in 2 periods will be reported.

The secondary endpoint of annualized weight-adjusted consumption of ~~factor~~/BPA injections will be summarized using descriptive statistics.

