- l* Sample may be used for study of biomarkers related to hemophilia and associated conditions, investigations of emerging safety issues, or the development of fitusiran. After specified analyses are run, residual samples may be stored for up to 15 years from last patient, last visit, or as per local regulations, and used for further study of biomarkers related to hemophilia and associated conditions, investigation of emerging safety issues, or the development of fitusiran. Samples drawn from central lines may be excluded from TG analysis.
- m* To be performed in all patients, at any clinic visit during their factor or BPA prophylaxis period, with blood drawn before, 10 min (± 5 min) after, and 60 min (± 5 min) after administration of their usual prophylactic dose of factor or BPA. Laboratory testing pre- and post- factor/BPA include: Coagulation, and TG. The timing of this visit should coincide with the patient's usual prophylaxis regimen, so that pre-dose thrombin generation is at nadir and the benefit of administered factor or BPA is maintained. For the United States specific requirements see [Section 11.6.1.1](#).
- n* On fitusiran dosing days, samples will be collected within 4 hour priors to dosing. For the AT assessments, upon the first AT level <15%, the patients must have another AT activity level sample drawn within 1 week of site receipt of the results.
- o* Liver function tests (LFTs) and hepatic tests are as listed in [Table 7](#). LFTs may be obtained up to 7 days before the clinic visit on which fitusiran dosing is scheduled. LFTs performed within 7 days of Day 1 will only be used to inform dosing on Day 1 and do not need to be used to confirm eligibility. LFTs can be analyzed locally, but if a local assessment is drawn, a serum chemistry sample must also be drawn for analysis at the central laboratory. Under conditions of elevated ALT and/or AST, see [Section 6.2.3.1](#) and [Table 8](#). LFT results will be obtained prior to receiving monthly fitusiran dosing.
- p* Blood samples for PK analysis will be collected at the time points listed in [Table 11](#) in East Asian patients at East Asian sites.
- q* Must be completed at clinic. Will be collected at EOS visit; not collected at ET visit.
- r* Perioperative assessment of safety and hemostatic efficacy only in patients undergoing major operative procedures while on study drug (see [Table 12](#)).

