Bleed Management Guidelines Day 8 and Beyond of Fitusiran Treatment Period:

When a patient experiences symptom that may be consistent with bleeding episodes, the following steps should be followed:

1. Patient should be instructed to call the study center to discuss symptoms to determine whether or not they are consistent with a bleeding event and to discuss the appropriate factor and/or BPA dose to use. This interaction between patient and Investigator is recommended prior to the administration of each dose of factor or BPA. Confirmation of bleeds at the study center prior to treatment may be considered. Such visits should capture assessments per [Section 6.4](#) and [Table 2](#).

2. If a determination is made that symptoms require treatment, the recommended treatment algorithm for bleeding episodes is described below:
 1. A single dose can be administered according to the guidelines in [Table 6](#).
 2. The patient should be instructed to re-evaluate symptoms in 24 hours for bleeds treated with FVIII, FIX or aPCC and in 2-3 hours for bleeds treated with rFVIIa.
 - a) Administration of FIX Extended half-life should not be more frequent than every 5-7 days.
 3. If a second dose (in the case of FVIII, FIX or aPCC) or a third dose (in the case of rFVIIa) is needed, the patient must call the study center before dosing.
 - a) Consider evaluation and treatment of the patient at the study center and confirmation of bleeds when any repeated doses are needed (See [Section 6.4](#) and [Table 2](#)).
 - b) If more than two doses of FVIII, FIX or aPCC or three doses of rFVIIa are needed, the patient should be seen at the study center within 48-72 hours.
 4. Doses should not be administered at less than 24-hour intervals (except rFVIIa as indicated in [Table 6](#)).
 5. Doses should not exceed the protocol maximum recommended dose indicated in [Table 6](#).
 6. Consultation with the study Medical Monitor and Clinical Advisor should be considered for clinical circumstances below, that may warrant AT replacement:
 - a) Doses of factor or BPA higher than those recommended in [Table 6](#)
 - b) Dosing of factor or BPA at decreased intervals than those recommended in [Table 6](#)
 - c) Multiple or repeated doses of factor or BPA
 7. Antifibrinolytics may not be used in combination with factor or BPA.

Table 6 - Bleed management dosing guidelines by specific product

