7.6.5 Clinical laboratory assessments

The following clinical laboratory tests will be evaluated by a central laboratory. Specific instructions for transaminase elevations are provided in Section 6.2.3.1. For any other unexplained clinically relevant abnormal laboratory test occurring after study drug administration, the test should be repeated and followed up at the discretion of the Investigator until it has returned to the normal range or stabilized, and/or a diagnosis is made to adequately explain the abnormality. Additional safety laboratories and assessments as indicated by the clinical situation may be requested. Clinical laboratory assessments are listed in Table 7 and will be assessed as specified in the Schedule of Assessments (Table 1).

While local laboratory results may be used for urgent clinical and dosing decisions, on the day of the clinic visit assessments, all laboratory assessments specified in Table 7 which are performed at the clinic should also be repeated at the central laboratory. In the case of discrepant local and central laboratory results on samples drawn on the same day, central laboratory results will be relied upon for clinical and dosing decisions.

Clinical laboratory assessments may be collected at the clinical site or at home by a trained healthcare professional. It is preferred that clinical laboratory assessments be drawn via peripheral draw (ie, fresh stick), however in cases where peripheral access is not possible existing indwelling venous access may be utilized.

Please see [Section 6.2.3.1](#) for the LFT monitoring and dosing plan.

Table 7 - Clinical laboratory assessments

| Hematology | |
|---|--|
| Hematocrit | Neutrophils, absolute and % |
| Hemoglobin | Lymphocytes, absolute and % |
| RBC count | Monocytes, absolute and % |
| WBC count | Eosinophils, absolute and % |
| Mean corpuscular volume | Basophils, absolute and % |
| Mean corpuscular hemoglobin | Platelet count |
| Mean corpuscular hemoglobin concentration | CD4 in HIV-positive patients (At Screening Only) |
| Serum Chemistry | |
| Sodium | Potassium |
| BUN | Phosphate |
| Creatinine and eGFR (using the MDRD formula) | Albumin |
| Glucose | Calcium |
| Chloride | Carbon dioxide |
| Liver Function Tests (LFTs) | |
| AST | ALP |
| ALT | Bilirubin (total and direct) |
| GGT | |
| Coagulation | |
| Prothrombin time | Activated partial thromboplastin time |
| INR | Fibrinogen |
| D-dimer | Prothrombin fragment 1, 2 |
| Factor Activity | |

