7.6.5.1 Additional laboratory assessments

For any safety event or laboratory abnormality, additional laboratory assessments, imaging, and consultation may be performed for clinical evaluation and/or in consultation with the study Medical Monitor; results may be collected and should be included in the clinical database.

Additional laboratory assessments will be performed in patients who experience any LFT abnormalities during either the factor or BPA prophylaxis period (BPA prophylaxis period is not applicable for the subgroup of Cohort A patients who are not responding adequately to BPA prophylaxis treatment) or the fitusiran treatment period. Following the occurrence of elevated liver transaminases or other LFT abnormalities per the central laboratory, all assessments in [Table 8](#) will be performed one time, as well as hematology, serum chemistry, LFT, and coagulation assessments from [Table 7](#), AT levels, and other assessments or evaluations per Investigator discretion, as appropriate. For the United States specific requirements, see [Section 11.6.1.2](#).

For patients in the fitusiran treatment period, monitoring and dose modification will also be performed as outlined in [Section 6.2.3.1](#).

Table 8 - Hepatic assessments in patients who experience LFT elevations

| Extended Hepatic Panel | |
|--|---|
| Herpes Simplex Virus 1 and 2 antibody IgM, IgG | Herpes Zoster Virus IgM, IgG |
| HIV 1 and 2 ^a | HHV-6 |
| Cytomegalovirus antibodies, IgM, IgG | HBs Ag, HBc antibody IgM and IgG |
| Anti-nuclear antibodies | Epstein-Barr Virus antibodies, IgM and IgG |
| Anti-smooth muscle antibodies | Anti-mitochondrial antibodies |
| HCV antibody | HAV antibody IgM |
| HCV RNA PCR – qualitative and quantitative | HEV antibody IgM |
| Imaging | |
| Abdominal ultrasound with Doppler flow (or CT or MRI) including right upper quadrant | |
| Focused Medical and Travel History | |
| Use of any potentially hepatotoxic concomitant medications, including over the counter medications and herbal remedies | Alcohol consumption |
| Other potentially hepatotoxic agents including any work-related exposures | Recent travels to areas where hepatitis A or E is endemic |

Note: All assessments will be measured in central laboratory. The full panel of assessments should only be performed once; individual assessments may be repeated, as needed

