11.6 COUNTRY-SPECIFIC REQUIREMENTS

11.6.1 United States

Change to the protocol for the United States only: new texts addition is presented as **bold** texts and deleted text is presented in ~~erossed~~ texts.

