Procedures for discontinuation of study drug and/or withdrawal from the study during the fitusiran treatment period are described in Section 5.3.1 and Section 5.3.2, respectively.

Section 6.3.1 ~~Factor Concentrates or~~ Bypassing agent prophylaxis

Section 6.3.1.1 Routine use of ~~factor or~~ bypassing agent prophylaxis in the ~~factor or~~ bypassing agent prophylaxis period

During the ~~factor or~~ BPA prophylaxis period, patients will continue to receive prophylaxis with their usual products on a regimen consistent with recommendations in the approved prescribing information, allowing for adjustment to individual patient response, and designed to decrease spontaneous bleeding. The regimen used during the ~~factor or~~ BPA prophylaxis period must have a minimum frequency of administration as presented in Table 4. The subgroup of Cohort A patients who are not responding adequately to BPA prophylaxis treatment will not participate in this BPA prophylaxis period and will directly start the fitusiran treatment period after the screening period.

Table 15 - ~~Factor or~~ Bypassing agent prophylaxis requirements

| Type of Factor or BPA replacement | Frequency of administration |
|--|-----------------------------|
| Standard half life FVIII | Twice weekly |
| Extended half life FVIII | Once weekly |
| Standard half life FIX | Once weekly |
| Extended half life FIX | Once biweekly |
| aPCC | Twice weekly |
| rFVIIa | Every other day |

Abbreviation: aPCC= activated prothrombin complex concentrates; BPA=bypassing agent; FVIII = ~~Factor VIII~~; FIX = ~~Factor IX~~; rFVIIa=recombinant Factor VIIa

Section 6.3.1.2 Management of ~~factor or~~ bypassing agent prophylaxis during the transition to the fitusiran treatment period

The first 28 days of fitusiran treatment is referred to as the onset period. During the onset period AT lowering will be progressing toward therapeutic levels. Patients will continue ~~factor or~~ BPA prophylaxis with minimum frequency as in Table 4, for the first 7 days of the fitusiran onset period. Subsequent to Day 7 of the fitusiran treatment period, ~~factor concentrates or~~ BPAs should be administered only for bleeding episodes or if needed in advance of invasive medical procedures.

Section 6.3.2 Management of bleeding episodes

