When a patient experiences symptoms that may be consistent with bleeding episodes, the following steps should be followed:

1. Patient should be instructed to call the study center to discuss symptoms to determine whether or not they are consistent with a bleeding event and to discuss the appropriate ~~factor and/or~~ BPA dose to use. This interaction between patient and Investigator is recommended prior to the administration of each dose of ~~factor or~~ BPA. Confirmation of bleeds at the study center prior to treatment may be considered. Such visits should capture assessments per Section 6.4 and Table 2.
2. If a determination is made that symptoms require treatment, the recommended treatment algorithm for bleeding episodes is described below:
 1. A single dose can be administered according to the guidelines in Table 5.
 2. The patient should be instructed to re-evaluate symptoms in 24 hours for bleeds treated with ~~FVIII, FIX or~~ aPCC and in 2-3 hours for bleeds treated with rFVIIa.
 - a) Administration of FIX Extended half-life should not be more frequent than every 5-7 days.
 3. If a second dose (in the case of ~~FVIII, FIX or~~ aPCC) or a third dose (in the case of rFVIIa) is needed, the patient must call the study center before dosing.
 - a) Consider evaluation and treatment of the patient at the study center and confirmation of bleeds when any repeated doses are needed (See Section 6.4 and Table 2).
 - b) If more than two doses of ~~FVIII, FIX or~~ aPCC or three doses of rFVIIa are needed, the patient should be seen at the study center within 48-72 hours.

4. Doses should not be administered at less than 24-hour intervals (except rFVIIa as indicated in Table 5).
5. Doses should not exceed the protocol maximum recommended dose indicated in Table 5.
6. Consultation with the study Medical Monitor and Clinical Advisor should be considered for clinical circumstances below, that may warrant AT replacement:
 - a) Doses of ~~factor or~~ BPA higher than those recommended in Table 5
 - b) Dosing of ~~factor or~~ BPA at decreased intervals than those recommended in Table 5
 - c) Multiple or repeated doses of ~~factor or~~ BPA
7. Antifibrinolytics may not be used in combination with ~~factor or~~ BPA.

Table 16 - Bleed management dosing guidelines by specific product

| | Factor VIII | Factor IX Standard half- life | Factor IX Extended half- life | aPCC | Recombinant Factor VIIa |
|--------------------------------------|---|---|---|---|---|

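### Eleven table pointers in the US appendix were not renumbered; the one with a residual effect is the US liver-test work-up rule, which cites Tables 7 and 6 instead of Tables 8 and 7

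*Protocol*

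**What the plan says.** Global Section 7.6.5.1 applies after raised transaminases or any other liver-test abnormality. It orders everything in Table 8 once, plus four routine test groups from Table 7, and it closes by sending US readers to Section 11.6.1.2. The US text there, under the old number 7.5.5.1, says that "all assessments in Table 7 will be performed one time, as well as hematology, serum chemistry, LFT, and coagulation assessments from Table 6".

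The current titles of the three tables are:

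- "Table 8 - Hepatic assessments in patients who experience LFT elevations"
- "Table 7 - Clinical laboratory assessments"
- "Table 6 - Bleed management dosing guidelines by specific product"

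The US appendix carries the same kind of number elsewhere. US Section 6.3.1.1 says that the prophylaxis regimen "must have a minimum frequency of administration as presented in Table 4". Item 5 of the bleed algorithm in US Section 6.3.2.2 reads: "Doses should not exceed the protocol maximum recommended dose indicated in Table 5". Table 4 is now the set of transaminase monitoring and dosing rules. Table 5 is now the list of minimum prophylaxis frequencies and contains no doses.

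**The concern.** US sites are told to use the US text. Followed to the letter, it replaces the one-time hepatic work-up with the routine laboratory list and takes laboratory tests from a table that holds only factor and bypassing-agent doses.

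The rule is operative safety text. Liver transaminase abnormalities, cholecystitis and symptomatic cholelithiasis are identified risks (Section 1.2.2.2), and cholecystitis and cholelithiasis are adverse events of special interest (Section 7.6.6.1). Table 8 includes abdominal imaging that covers the right upper quadrant, so a site that did not reach Table 8 would not be told to do that imaging.

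The cap on bleed-treatment doses is one of the protocol's thrombosis precautions (Section 1.5). It should cite the table that contains it.

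**Working it through.** No formula applies. The check compares each table pointer in Section 11.6.1.2 with the current table titles and with the matching global sentence. Pointers to Tables 1 and 2 are correct and are left out.

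| US text | Cites | Subject meant | Current number | US copy | Pointers |
|---|---|---|---|---|---|
| 6.3.1.1 and 6.3.1.2 | Table 4 | prophylaxis frequency | Table 5 | Table 15 | 2 |
| 6.3.2 | Table 5 | bleed dosing | Table 6 | Table 16 | 1 |
| 6.3.2.2 | Table 5 | bleed dosing | Table 6 | Table 16 | 6 |
| 7.5.5.1 | Table 6 | routine laboratory tests | Table 7 | none | 1 |
| 7.5.5.1 | Table 7 | hepatic work-up | Table 8 | none | 1 |

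The total is 2 + 1 + 6 + 1 + 1 = 11. In every row the current number minus the cited number is 1.

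**Likely cause.** The history of amendment 05 (Section 11.7.5) records a new Table 3, which would move each later table up by one. I use the history only to explain the pattern. The mismatch itself lies within the current text.

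**What the literal liver rule leaves out.** The Table 8 laboratory panel has 14 items. Five also appear in Table 7: HAV IgM, HEV IgM, HCV antibody, HCV RNA and, in part, the hepatitis B item. That leaves 14 − 5 = 9: herpes simplex, herpes zoster, HIV, HHV-6, CMV, EBV, and anti-nuclear, anti-smooth-muscle and anti-mitochondrial antibodies. The imaging item and the 4 history items are also left out. The count of 9 is approximate, because HBsAg is not in the hepatitis B row of Table 7 as extracted, although the table's footnote defines it.

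**What other text restores.**

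- Table 1 footnote o has no US replacement. It opens a cross-reference with "Under conditions of elevated ALT and/or AST" and sends the reader to Section 6.2.3.1 and Table 8.
- Table 4 has no US replacement either. It orders Table 8 for confirmed isolated ALT or AST elevations from above 3× to 8× ULN.
- Table 7 lists 5 liver analytes: AST, ALT, ALP, GGT and bilirubin. These two routes cover AST and ALT, so 5 − 2 = 3 remain (ALP, GGT and bilirubin) when one of them is abnormal without a raised ALT or AST.

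**The nine other pointers.** US Table 15 is printed between the two pointers that should cite it. US Table 16 follows directly after the bleed algorithm.

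**The case against.** The strongest reply is that nobody would follow the literal text. Table 7 already contains hematology, chemistry, liver tests and coagulation, so the second clause of the US rule would be redundant. Table 6 contains no laboratory test at all. Table 8 announces its purpose in its title, is not limited there to ALT and AST, and is not replaced in the US section. The heading number 7.5.5.1 no longer exists, so the copy visibly carries old numbering. The rule also leaves further tests to the investigator. All of this stands, and it is why the effect is small. It does not make the sentence correct, and the rule's own trigger covers liver-test abnormalities other than transaminases.

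A second reply concerns exposure. If amendment 05 caused the shift, 79 patients were already enrolled by then (Section 11.7.5), and SAP Section 2.4 reports only 2 participants on 50 mg Q2M. That suggests that few US patients on fitusiran were managed under the wrong numbers. The documents do not say how many of these patients were in the US, nor how many were still in the prophylaxis period, where the rule also applies.

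A third reply concerns intent. Section 11.6.1 introduces marked edits with "Change to the protocol for the United States only", and the table numbers show no mark. That is weak evidence, because bold and strike-through survive unevenly in the extracted text. The uniform shift of one and the citation of a dosing table for laboratory tests are better evidence of a slip.

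**Conclusion.** The point holds as a minor inconsistency. Eleven US table pointers are stale, and only the two in the liver work-up rule leave a gap. That gap is an isolated bilirubin, ALP or GGT abnormality in a US patient, where the literal text does not order the Table 8 panel, imaging or history. This assumes that footnote o and Table 4 apply to US sites, as they do unless replaced.

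A reader might infer four stronger things that the documents do not support:

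- **That US patients with raised ALT or AST lose the hepatic work-up.** Footnote o and Table 4 still order it.
- **That the US text deliberately prescribes a different panel.** Nothing suggests a reason for one, and Table 6 could not supply it.
- **That US sites would apply a wrong dose cap.** Table 5 holds no doses, and the correct caps are in Table 16 beside the algorithm.
- **That the eleven are the only stale references.** They are the table pointers in the US text. Other references are stale too, and I give no total for them because my list under the fix is not exhaustive.

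No dosing threshold, stopping rule, endpoint, sample size or analysis is affected.

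**What to change.** In Section 11.6.1.2:

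- US 7.5.5.1: change Table 7 to Table 8, and Table 6 to Table 7.
- US 6.3.1.1 and 6.3.1.2: change Table 4 to Table 15 (2 places).
- US 6.3.2 and 6.3.2.2: change Table 5 to Table 16 (7 places).

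Correct the other stale references in the same pass, after a full search. Examples are:

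- US text: section numbers 7.5.5.1 and 7.5.6.1, which are now 7.6.5.1 and 7.6.6.1; and the literature citations in US 6.3.2 (2, 7, 8, where the global text has 3, 13, 14).
- Headings of global 6.3.2.2 and 6.3.2.3, and their contents entries: Appendix 11.5.1.2, which is now Section 11.6.1.2.
- Japan (Section 11.6.2): the bleed-dosing heading numbered Table 5 (now Table 6); Section 10.1.5, although Section 10 is the reference list; Section 8.4, although Section 8 is Statistics and has only 8.1 and 8.2; and references 16 and 17 for factor half-life, which are now the sepsis and intravascular coagulation guidelines.

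The cost is editorial only. If the amendment is delayed, a short clarification of the liver rule to US sites would close the one gap that remains.
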